The unilateral exercise will be performed using seated single knee extension exercise against resistance. Subjects will be seated with the hips flexed at 90° with their back against a backrest at a ≈110° angle. The leg pad will be positioned ≈5 cm above the ankle and the rotation arm will be positioned so that the knee is bent to 90°. After a warm-up consisting of 8-10 repetitions with minimal resistance, the weight will be adjusted to 70% of the one repetition maximum. The unilateral 1-RM will be determined by a post-training period strength test, performed on a different day. Five sets of 10 repetitions will be performed, with 2 minutes of rest periods between sets. The load will be adjusted during the course of the session due to fatigue such that each subject is able to perform 10 repetitions during each set.

The supplement, high-calorie whey, (300 ml) comprises 24 g whey protein (contains ≈3 g leucine) with 30g carbohydrates (sucrose) in liquid, and the placebo contains a liquid, dextrose 24 g plus sucrose 30g. The amount of whey (Nestle Healthcare) prescribed is guided by studies in normal subjects (66; 69; 70; 110) including the elderly (70; 74). We do not anticipate any adverse effects from nutrient or placebo if taken as prescribed. Whey has a low NA, K and phosphorus content (60,140 and 60 mg/serving respectively). The vehicle for dissolving the powdered supplement will be of the subject's choice, but is limited to fluids permissible for ESRD such as apple juice and will be pre-tested for taste by the subject. Whey is also available in a variety of flavors and in long term studies has been included in baked goods or sprinkled over foods.

Detailed molecular analysis of skeletal muscle. The following items will be measured using methods established in [name] laboratory. Note that receptor and signaling proteins will be measured by western immunoblots; mRNA levels by real-time quantitative PCR, and selected degradative proteins by immunoblotting and serum and local IGF-1 by ELISA.

- mRNA levels of local regulators of muscle mass: Total IGF-1 (all transcripts), the Ea transcript (a generalized tissue form and main form in liver, and the IGF-1Eb transcript, MGF, a loading sensitive and more potent form than the Ea form). Myostatin, and receptors for IGF-1, insulin, growth hormone and androgens.
- mRNA levels of inflammatory cytokines IL-6 and TNF α .

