Secondary analyses, Specific Aim 2. In this specific aim we will analyze molecular changes in muscle biopsied at baseline and at the end of the study. IGF-1 is a key muscle growth factor; Kopple et al (45) reported that IGF-1Ea mRNA levels rose ~100% in 12 MHD subjects undergoing 21.5 weeks of combined resistance and endurance exercise. We plan to compare changes in IGF-1 mRNA levels from baseline to those levels at the end of 12 weeks of rehabilitation or usual care. Muscle will be obtained from limbs at rest in the exercise and usual care subjects as described above (n=12/group) and we will consider a 50% change in IGF-1Ea mRNA to be a clinically meaningful difference. While there are no data available in MHD subjects to estimate the standard deviation of the change in these molecular indices from baseline, Appendix VIII may be used to estimate the power associated with an assumed standardized effect size that is small (0.3), medium (0.5) or large (0.8).

Secondary analyses, Specific Aim 2A. In this specific aim we will assess the nutrient-enhanced exercise-induced protein signal transduction pathway in subjects undergoing exercise versus usual care. Specifically, we will compare the change in activity (phosphorylation) of the mTOR signal transduction pathway induced by unilateral exercise alone versus unilateral exercise plus nutrient supplementation. This will be a pilot study of 12 subjects in each group. Since this is a novel measurement and there are no data in MHD subjects describing the variance of this response, a power analysis has not been carried out. Change in activity will be taken to equal the difference in activity between the unilateral exercise limb and the contra-lateral resting limb of the same subject. We will also examine the effect of the supplement alone vs. placebo on signal transduction in the resting limb of unilateral exercise and usual care subjects. Of note, Hulmi (71) reported that whey protein enhanced exercise-induced signaling (phosphorylated p70S6K)

by nearly 5-fold over exercise alone in young healthy subjects, while Drummond (73) noted a similar increase in the elderly following EAA ingestion.

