Statistical analysis plan. Comparisons of clinical and demographic data between groups at baseline will be performed by the appropriate statistical test (for continuous variables, t-test for normally distributed data and Wilcoxon test for non-normal data; for categorical variables, chi-square test or Fisher's exact test). These comparisons will be performed at baseline only to assess adequacy of randomization. Comparisons between groups for cardiopulmonary exercise test, muscle biopsy, energy expenditure, cognitive function, and other functional measures before and after the study period will be performed by multivariate ANOVA; post-hoc comparisons will be made using the Bonferroni method. To analyze continuous variables measured at three or more time points we will use linear mixed effects regression (114). To explore the relationships between a given outcome and other variables, we will use multiple regression techniques. Since the reliability of a fitted regression model may be reduced if too many predictors are used (114), we will limit the number of predictors to four variables in each model ($\leq 1/10$ of the total). For the primary outcome, change in peak VO_2 , the specific independent variables in the model will include exercise compliance (average energy expended in kcals/week), change in muscle strength, and change in muscle mass. Missing data will be managed using the multiple imputation method which is preferable to older methods and described in detail by Schafer & Olsen (1999).

For Specific Aim 2 (effect of acute and chronic exercise on muscle wasting), we will employ a linear model, using period (baseline vs. 4 months) and treatment (exercise training vs. usual care) as independent variables along with their interaction (Bonferroni method). The intention to treat principal will be applied for all analyses.

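### IGF-1Ea mRNA has a 50% criterion, but the planned model compares changes in level with no stated log scale and no baseline covariate; a baseline-adjusted log-scale model would give the ratio directly

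*Combined protocol and SAP*

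**What the plan says.** Under Secondary analyses, Specific Aim 2, the plan cites a study in which "IGF-1Ea mRNA levels rose ~100% in 12 MHD subjects" and sets its own threshold: "we will consider a 50% change in IGF-1Ea mRNA to be a clinically meaningful difference". Both figures are relative. The contrast is described as "We plan to compare changes in IGF-1 mRNA levels from baseline" to the end of the 12 weeks, exercise against usual care, with 12 subjects per group. The same paragraph concedes that "there are no data available in MHD subjects to estimate the standard deviation of the change in these molecular indices from baseline" and refers the reader to the general power curves in Appendix VIII.

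The Statistical analysis plan adds, for Specific Aim 2: "we will employ a linear model, using period (baseline vs. 4 months) and treatment (exercise training vs. usual care) as independent variables", together with their interaction. (The period label differs from the 12-week endpoint; that is a separate matter.) The same section also lists muscle biopsy among the measures compared by multivariate ANOVA. No transformation, fold change or ratio is named for mRNA, and the baseline level is not used as a covariate. The only provision for non-normal data, the Wilcoxon test, is confined to the baseline comparisons. The laboratory section specifies "mRNA levels by real-time quantitative PCR" but gives no scale for analysis.

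**The concern.** The threshold is a proportion, whereas the fitted quantity, on the natural reading of the text, is an additive difference in assay units. A reader of the results would need a further step to tell whether the 50% was reached, and the plan does not describe one. Different steps give different answers: dividing by the mean baseline is not the same as averaging subjects' percent changes. The plan also does not say whether the 50% refers to the change within the exercise group or to the contrast with usual care.

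The second issue is efficiency. With 12 per group there is little information to spare, and the baseline biopsy is already taken. An analysis of raw change uses that value less well than one that takes logs and adjusts for it.

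**Working it through.** **Inputs from the documents.** Criterion 50%; earlier rise about 100%; 12 per group; no SD of change. The two-sided 0.05 level is the one stated for the primary endpoint.

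**Assumptions.** Levels are lognormal. The SD of the log level (log SD) is 0.4, 0.6 or 0.8, equal in both groups and at both times. The correlation ρ between log baseline and log end value is 0.3, 0.5 or 0.7. Usual care does not change; exercise multiplies the level by r. The planned model is taken to pair each subject's two biopsies, so that its interaction is the difference in mean change.

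**Step 1: the plan's own figures.** The primary calculation uses 17/20 = 0.85. A two-sample t-test then needs 22.7, so 23 per group, as stated. At 23 per group, power is 0.169 and 0.382 for standardized effects of 0.3 and 0.5, against the stated 0.17 and 0.38. These reproduce. At the 12 per group used for IGF-1Ea, power is 0.11, 0.22 and 0.47 for effects of 0.3, 0.5 and 0.8. The plan ties none of these effects to a 50% change, so there is no IGF-1Ea power to reproduce.

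**Step 2: what the interaction estimates.** With mean baseline m in both groups, interaction = (r − 1) × m. For r = 1.5 this is 0.25, 0.5 and 1.0 units at m = 0.5, 1 and 2. Dividing by m returns 0.50 each time, and in simulation it returned 0.50 in all nine combinations of log SD and correlation.

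If usual care also moves, the choice of contrast matters. Suppose exercise rises 20% and usual care falls 20%. The ratio is 1.2/0.8 = 1.5, but interaction/m = 1.2 − 0.8 = 0.4.

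**Step 3: averaging percent changes instead.** The expected end/baseline ratio is r × exp(SD²(1 − ρ)), so the between-group difference in mean percent change is (r − 1) × exp(SD²(1 − ρ)). For r = 1.5:
- log SD 0.4, ρ 0.7: 0.5 × exp(0.16 × 0.3) = 0.5 × 1.049 = 0.52
- log SD 0.8, ρ 0.3: 0.5 × exp(0.64 × 0.7) = 0.5 × 1.565 = 0.78

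Conversely, an average difference of 50 points needs a true ratio of 1 + 0.5/1.049 = 1.48 in the first case but only 1 + 0.5/1.565 = 1.32 in the second.

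**Step 4: power at 12 per group, ρ = 0.5** (20,000 simulated trials per setting).

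| True r | Log SD | Raw change | Raw level, raw baseline covariate | Log change | Log level, log baseline covariate |
|---|---|---|---|---|---|
| 1.5 | 0.4 | 0.677 | 0.721 | 0.662 | 0.765 |
| 1.5 | 0.6 | 0.333 | 0.362 | 0.356 | 0.435 |
| 1.5 | 0.8 | 0.178 | 0.193 | 0.226 | 0.267 |
| 2 | 0.4 | 0.989 | 0.988 | 0.980 | 0.995 |
| 2 | 0.6 | 0.760 | 0.774 | 0.776 | 0.863 |
| 2 | 0.8 | 0.453 | 0.476 | 0.533 | 0.627 |

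Over all 18 settings with a true effect (two ratios, three log SDs, three correlations), the log model with baseline was at least as powerful as raw change. The gain ran from nil to about 19 points (0.355 to 0.547 at r = 2, log SD 0.8, ρ = 0.3). The scale change alone ran from −3 points (0.540 to 0.511 at r = 1.5, log SD 0.4, ρ = 0.3) to +13 (0.618 to 0.752 at r = 2, log SD 0.8, ρ = 0.7). With no true effect, rejection rates for raw change, log change and the log model with baseline lay between 0.041 and 0.053.

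**The case against.** The strongest reply is that the plan leaves the scale open. A linear model can be fitted to logs, nothing in the text excludes that, and change in the primary endpoint is expressed as a percentage. That stands: the scale is unstated, not fixed as raw. It does not settle the matter, because the percent-change reading has the distortion in Step 3, and no reading of the text brings in the baseline covariate.

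Three stronger readings are tempting, and the documents do not support them.
- A reader might infer that the planned model cannot be set against 50% at all. Step 2 shows that one division recovers it when usual care is stable and the effect is multiplicative.
- A reader might note that, with no true effect, mean percent change within one arm is exp(SD²(1 − ρ)) − 1, or +5% to +57% over the assumed range, and conclude that the comparison is biased. The shift is the same in both arms and cancels between them. It would mislead only if the 50% were judged within the exercise arm.
- A reader might conclude that skewed levels always cost power. The scale change alone is slightly harmful at low spread, and much of the gain in Step 4 appears only when the covariate is added on the log scale.

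It is also fair to say that the plan attaches no decision rule to the 50%.

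**Conclusion.** The concern holds in a limited form. A relative criterion is paired with an analysis whose stated form yields an additive effect, and the route from one to the other is not given. The routes a reader might take do not agree: a true 1.5-fold effect reads as 50% after division by mean baseline, but as 52% to 78% from averaged percent changes. A baseline-adjusted log-scale model avoids the choice and, under the assumptions above, is never less powerful than raw change. At ρ = 0.5 it adds about 9 to 10 points for a 1.5-fold rise and about 1 to 17 points for a two-fold rise.

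The power figures depend on an assumed lognormal form and assumed spread and correlation, because the documents give no variance; the largest gains need the upper end of the assumed spread. The mismatch between criterion and fitted effect needs none of those assumptions. This is a secondary molecular outcome of pilot character. Neither the primary peak VO₂ comparison nor the sample size is affected, so this is a worthwhile refinement, not a serious fault.

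**What to change.** For IGF-1Ea and the other mRNA outcomes, specify a model for the log of the end-of-study level with treatment group as factor and log baseline level as covariate. Back-transform the group coefficient and report the exercise/usual-care ratio of geometric means with its 95% interval. State that the 50% criterion applies to this between-group contrast and corresponds to a ratio of 1.5.

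The cost is a few lines in the Statistical analysis plan and one degree of freedom: with 12 per group, residual degrees of freedom fall from 22 to 21. No extra subjects, biopsies or assays are needed. If only the scale were changed and the covariate left out, power could fall by about 3 points where levels vary little, so the two changes should be made together.

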General study design: MHD subjects aged 65-80 years with impaired exercise capacity and function will be randomized into two groups (30/group). One group will undergo a home-based exercise program and the other usual care over a 12 week period. This subject number allows for a drop-out rate of 20%, while maintaining 80% power to detect a significant difference in our primary end-point, peak VO_2 . After enrollment, all subjects will be encouraged to consume at least 1.2 g/kg/protein/day throughout the study. The 12-week program will include a 2-week clinic-based exercise instruction period with testing at baseline before intervention and after 6 and 12 weeks. Measures at baseline and 12 weeks will include body composition by anthropometrics and dual energy X-ray absorptiometry (DEXA), thigh muscle volume and composition by CT scan, muscle strength and function, cardiopulmonary exercise testing, QOL, cognitive function and nutritional, inflammatory, lipid and biochemical status. Muscle biopsies will be obtained at baseline and at 12 weeks and will be assayed for signaling proteins, and gene and protein expression of key muscle mass regulators. More limited interim testing will be performed at 6 weeks. In addition, two to three days after the 12-week study, a pilot sub-study will be performed to test whether a high-calorie leucine-rich protein supplement enhances exercise-stimulated anabolic signaling. At this time muscle biopsies will be taken. Overviews of the study measurements and timeline are presented in Appendices I and II.

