A. Specific Aim 1 is designed to develop an effective, safe, low-cost aerobic and resistance exercise regimen. Because of the focus on improving cardiopulmonary function as well as muscle function and mass, both resistance and aerobic exercise will be components of the rehabilitation program. The program is modeled on a successful combined in-home/in-center study program administered by [name] at the VAPAHCS rehabilitation center for patients with cardiovascular disease with a mean age of 72 years (87). In general, exercise rehabilitation is highly effective in patients with cardiovascular disease (76), including the elderly (77; 78), and is associated with improved survival rates (76; 77; 79). Subjects randomized to the exercise group will undergo 12 weeks of exercise, including a 2-week ramp-up period conducted at the VAPAHCS rehabilitation facility. Subjects will be required to attend the facility twice a week on non-dialysis days during the initial 2 weeks of the study. These sessions will consist of 45-60 min of supervised exercise that combines aerobic and resistance training, including warm-up and cool-down. Throughout the study, subjects will be asked to perform 45 minutes of unsupervised aerobic exercise of their choice (such as walking) on non-dialysis days. Following the initial 2-week supervised period, subjects will be instructed to exercise on their own, and surveillance methods will be employed as previously described (87; 93) and outlined below. Following the 12-week study period, all subjects will undergo muscle biopsies. The following end-points will be measured at baseline and after the 12 week study period:

Primary Endpoint. Peak VO₂ is the primary outcome measure and is the gold standard for cardiopulmonary fitness. It incorporates elements of cardiac, pulmonary and muscle function known to improve with exercise.

Secondary Endpoints. These include lower and upper body strength, body composition, thigh muscle mass, muscle biopsy for protein signaling, quantitative muscle morphology and gene expression, daily activities, QOL, laboratory measures of cardiovascular risk factors, nutritional and inflammatory parameters as detailed below.

Together, these measures should allow us to determine whether the home-based exercise regimen is effective in counteracting loss of muscle function and mass common in elderly MHD patients, along with reducing cardiovascular risk.

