Since this is a pilot sub-study carried out with a limited number of subjects after completion of the main 12 week study, we have adopted a unilateral exercise protocol in which the resting contralateral limb serves as a control. This protocol will allow us to gain considerable insight into the salutary molecular processes activated by exercise in ESRD subjects and to test whether these processes can be enhanced by provision of a leucine-rich supplement. In brief, two to three days after completing the primary 12-week study, subjects from both the exercise and usual care groups will be studied in which one limb is exercised for 15 minutes, after which the vastus lateralis muscles of both the exercised and the contralateral resting limb will be biopsied. *Half the subjects in each of these 2 main groups (12 subjects from each group) will be matched by BMI and age and randomized to either a placebo mixture or a high calorie nutrient supplement.* The nutrient supplement will consist of a high-calorie leucine-rich protein (whey protein) given at the start and end of the exercise session. The study consists of the following 4 groups, each undergoing acute, unilateral exercise:

- Group 1.** Regular exercise group plus placebo
- Group 2.** Regular exercise group plus nutrient supplement
- Group 3.** Usual care group plus placebo
- Group 4.** Usual care group plus nutrient supplement

An outline of the experimental protocol is illustrated in Figure 2, and a detailed protocol follows.

[figure not shown]
Figure 2. Acute Exercise, Muscle Biopsy, and Nutrient Supplement Protocol for Specific Aim 2

Biopsies will be obtained from the dominant limb after acute exercise and from the non-dominant limb following rest. A *single* biopsy of each limb will be taken from each subject. Tissue taken from the biopsies will undergo molecular analysis to answer the following questions:

[figure not shown]

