1. What sustained molecular processes, activated by regular exercise, might be contributing to the maintenance or improvement of muscle mass in MHD subjects who participate in a 12 week exercise program? To this end, molecular events in the *resting* dominant limb of participants given placebo in regularly exercised (Group 1) and usual care (Group 3) subjects will be compared. We will test the postulate that regular exercise acts largely by inducing local changes in the expression of key regulators of muscle mass and also by stimulating the Akt/mTOR signaling pathways that serve to promote protein synthesis and inhibit proteolysis. We anticipate that a 12-week program of rehabilitation will increase muscle mass as measured by CT and DEXA scans, and improve skeletal muscle function via several interrelated mechanisms. These include changes in the balance between IGF-1 and myostatin, increased androgen receptor expression, changes in expression of components of the ubiquitin-proteasome and calpain proteolytic systems, suppression of inflammatory cytokines, and increased anabolic signaling. This is illustrated in Figure 3.

Figure 3. Assessment of 12 weeks of exercise training vs. usual care in resting muscle among subgroups receiving placebo.

2. What impact does acute exercise have on anabolic signaling in regular exercise versus usual care subjects? To answer this question we will measure activity (phosphorylation) of the IRS-1/AKT and mTOR signaling transduction pathways in the *acutely exercised* (and the contralateral resting) limbs of regular exercised subjects ingesting placebo (Group 1). The same measurements will be made in the muscle of the corresponding usual care group (Group 3) (Figure 4). Activity of the anabolic IRS-1/AKT and mTOR signaling pathways in the exercised limb will be compared with these responses in the contralateral resting limb of the same subject. We anticipate that acute exercise will activate anabolic signaling in both groups and that the response will be more vigorous in the regular exercise group.

[figure not shown]
Figure 4. Assessment of the response to acute exercise in trained vs. usual care subjects

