Primary endpoint, Specific Aim 1. For this analysis we have used data from a recent 12-week study by Storer et al (36) on the effects of endurance exercise versus no exercise (usual care) on cardiorespiratory and skeletal muscle function in MHD patients. Change from baseline for peak VO₂ was 22% (an increase) in the exercise group and 6% (a decrease) in the usual care group. These findings are consistent with an average increase from baseline of 17% in MHD patients participating in exercise-based rehabilitation programs reported in the literature (14). Similarly, our primary outcome will be comparison of the change in peak VO₂ for patients randomized to exercise vs. usual care. To calculate the desired sample size we used a two group t-test of equal means and calculated the per group sample size (East 5, Cytel Inc, copyright 2007). Given the desired values for the standardized effect size (the absolute value of the difference in group mean changes divided by the common standard deviation) and overall level of significance and power of the test, the required sample was calculated. To detect a difference in group mean changes of 17% in peak VO₂ for exercise vs. usual care, given a common standard deviation of 20% (based on Storer et al (36), using a standardized effect size of 0.85), 23 subjects/group would be required to complete the study to achieve statistical power of 80% with a two-sided test of significance at the 0.05 level. Appendix VII shows how the required sample size varies by the standardized effect size for power of 0.80 (solid curve) and 0.85 (dashed curve). Appendix VIII provides curves showing how the power varies by the standardized effect size for a per group sample size of 23 (solid curve) and 26 (dashed curve). For example, a per group sample of 23 provides power of about 0.17 and 0.38 to detect a small (0.3) and medium (0.5) standardized effect size, respectively. To allow for a 20% dropout rate we plan to enroll 30 subjects per group, or a total of 60. The 20% dropout rate is based on the PI's experience (87), and other similar research studies.

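### Power for Aim 2, stated at 12 per group, is to be read from curves for 23 and 26 per group; at a standardized effect of 0.8 they show 0.76 to 0.81 where 12 per group gives 0.47

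*Combined protocol and SAP*

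**What the plan says.** Under Secondary analyses, Specific Aim 2, the plan compares the change in muscle IGF-1 mRNA from baseline to 12 weeks, using resting muscle obtained "in the exercise and usual care subjects as described above (n=12/group"). A 50% change in IGF-1Ea mRNA is taken as clinically meaningful. No standard deviation of the change is available for these patients, so instead of a calculation the plan says that "Appendix VIII may be used to estimate the power associated with an assumed standardized effect size" that is small (0.3), medium (0.5) or large (0.8).

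The paragraph just before it, Primary endpoint, Specific Aim 1, describes that appendix as power curves "for a per group sample size of 23 (solid curve) and 26 (dashed curve").

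Four other places bear on how many subjects enter the Aim 2 comparison:

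- B. Approach to Specific Aim 2 describes the supplement randomisation: "Half the subjects in each of these 2 main groups (12 subjects from each group").
- Question 1 of that section says molecular events in the resting "limb of participants given placebo in regularly exercised (Group 1) and usual care (Group 3) subjects will be compared".
- General study design says "Muscle biopsies will be obtained at baseline and at 12 weeks", and A. Specific Aim 1 says that after the 12 weeks "all subjects will undergo muscle biopsies". Neither names a subset.
- The Aim 2 model in the Statistical analysis plan uses period and "treatment (exercise training vs. usual care) as independent variables along with their interaction", with no restriction to placebo subjects.

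Item (1) of the limitations section calls the study adequately powered for its aims in general, not only for the primary endpoint.

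**The concern.** Power at a given standardized effect depends on the group size. A curve for 23 or 26 per group cannot give the power of a comparison with 12 per group, and the documents describe no curve or figure for 12.

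A reader who follows the instruction at the large effect obtains about 0.76, close to the 80% planned for the primary endpoint, and would take Aim 2 to be nearly as well powered. At 12 per group a true effect of that size would be missed about 53% of the time (1 − 0.466 = 0.534). A null IGF-1Ea result could then be read as evidence that training does not act through this pathway, when the comparison had little chance of showing that it does.

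**Working it through.** **Inputs.** Group sizes of the Appendix VIII curves: 23 and 26 (Primary endpoint, Specific Aim 1). Aim 2 group size: 12. Standardized effects d: 0.3, 0.5 and 0.8 (both from Secondary analyses, Specific Aim 2). Test: two-group t-test, two-sided 0.05. The plan states this for the primary endpoint; it is assumed here for Aim 2, where no level is given. The appendix figure is not in the available text, so its curves are recomputed from the group sizes given for it.

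**Formula.** With n per group, T has a noncentral t distribution with 2n − 2 degrees of freedom and noncentrality d × √(n/2). Power is P(|T| > t(0.975, 2n − 2)).

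**Reproducing the plan's own figures.** For d = 17/20 = 0.85 and 80% power the formula gives n = 22.73, hence 23 per group, as stated. At n = 23 it gives 0.169 for d = 0.3 and 0.382 for d = 0.5; the plan prints 0.17 and 0.38. One-sided versions give 0.26 and 0.51 and do not match. The method behind the curves is therefore identified.

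**Power by group size.**

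| n per group | d = 0.3 | d = 0.5 | d = 0.8 | d for 80% power |
|---|---|---|---|---|
| 23 (solid curve) | 0.169 | 0.382 | 0.756 | 0.84 |
| 26 (dashed curve) | 0.186 | 0.424 | 0.807 | 0.79 |
| 12 (stated for Aim 2) | 0.108 | 0.216 | 0.466 | 1.20 |
| 24 (all completers) | 0.175 | 0.396 | 0.774 | 0.83 |
| 6 (if 12 per arm are split by supplement) | 0.076 | 0.123 | 0.241 | 1.80 |

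For example, at d = 0.8 the noncentrality is 0.8 × √6 = 1.96 for n = 12 and 0.8 × √11.5 = 2.71 for n = 23.

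**Size of the overstatement for n = 12.** The 23-per-group curve is too high by 0.061, 0.166 and 0.290 at the three effects. The 26-per-group curve is too high by 0.077, 0.208 and 0.342.

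**Where 12 comes from.** 30 per arm less 20% dropout is 30 × 0.8 = 24. Half of these receive placebo: 24/2 = 12 per arm. That is the Group 1 versus Group 3 contrast, so the stated 12 fits the design.

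**Precision.** The half-width of a 95% confidence interval for the difference, in SD units, is t(0.975, 2n − 2) × √(2/n): 0.85 at n = 12 and 0.58 at n = 24.

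**The case against.** The mismatch itself is hard to dispute; the case against concerns what follows from it.

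*The plan miscalculates nothing.* This is true. The printed 0.17 and 0.38 are correct for 23 per group, and no Aim 2 power is printed. The defect is a cross-reference that gives the wrong answer when followed.

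*The group sizes of the curves are stated one paragraph earlier, so a careful reader would not be misled.* Possibly, but that reader is then left with no usable source of power at 12 per group, and the instruction remains wrong.

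*Perhaps all completers are meant.* This is the strongest point. General study design, A. Specific Aim 1 and the Aim 2 model do not restrict the biopsies or the analysis to a subset. Question 1 of the Aim 2 approach also compares resting muscle between placebo groups after training, whereas the power paragraph concerns change from baseline, so the two need not use the same subjects. At 24 per arm the power for d = 0.8 is 0.77 and the 23-per-group curve is nearly right. On the other side, the Retention section pays extra to participants in a biopsy substudy, and the Aim 2 approach refers to a limited number of subjects. Both favour 12. If the 12 from each main group are themselves divided by supplement, 6 remain per cell and the curves fit worse still. On every reading the Aim 2 paragraph needs a correction.

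*It is a pilot, and the 80% claim is tied to the primary endpoint.* That limits the consequence and stands. Yet for Aim 2A the plan says openly that it made no power analysis, while for Aim 2 it offers a source that does not fit.

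**Conclusion.** The concern holds. As written, the Aim 2 paragraph combines 12 per group with power curves for 23 and 26, and following it at d = 0.8 gives 0.76 to 0.81 instead of 0.47. The mismatch is certain; the figure of 0.47 is conditional on 12 being the analysed number. If about 24 per arm is meant, the group size is the error and the pointer is nearly right.

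The figures assume an unadjusted two-sided 0.05 t-test. A one-sided 0.05 test would give 0.60 at 12 per group, still well below the curves. The Bonferroni adjustment named with the Aim 2 model could only lower power. The analysis is secondary and exploratory; the primary sample size and result are untouched.

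**What to change.** State how many subjects per arm enter the baseline-to-12-week IGF-1Ea comparison, and make the Aim 2 approach, the power paragraph and the Aim 2 model agree on it.

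- If it is 12 per arm (placebo subjects, Group 1 versus Group 3), replace the pointer to Appendix VIII with a 12-per-group curve or with the figures: power 0.11, 0.22 and 0.47 at d = 0.3, 0.5 and 0.8, and 80% power only at d of about 1.20. Add the placebo restriction to the model.
- If all completers are meant, correct the group size to about 24 and give 0.17, 0.40 and 0.77.

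In either case confine the general statement of adequate power in the limitations section to the primary endpoint. It would also help, though it is not needed to correct the error, to report Aim 2 as estimates with 95% confidence intervals.

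The cost is a few sentences and perhaps one added curve, with no further patients or biopsies. The downside is that, if 12 is confirmed, the stated power for Aim 2 becomes less favourable.
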